3.2. Processing and Security aspects for patient data during testing

(for detailed description of data transfers- see section 1)

- 4 = data transfer from Hospital production system to AIDAVA
- 5 = data transfer from HDI to AIDAVA@hospital
- 6 = data transfer from AIDAVA@hospital to HDI (IPS and potentially full PHKG)

Question	Answer from Data HOLDER
Transmission method.	 Frequency of the exchange If 4 or 5 = Once at the beginning of testing of each generation of the prototype (push from hospital systems into the file share within VPN). Data of each patient will be transferred independently. If 6 = Twice during the evaluation period by a patient: after week 1 and after week 2. Data exchange will be incremental (for 4 and 5): exchange of any data source should be complete, additional data sources can be exchanged as they become available during evaluation. Security classification and level of risk of the data: SENSITIVE data including personal identifiable data
Transmission encryption (If data encryption is required, what encryption method will be used?)	 If 4 = (to be specified by each hospital) MAASTRO/MUMC: HTTPS based using SSL If 5 = For MIDATA (NEMC, MUG): Data traffic from and to server via HTTPS, TLS 1.3. Connection and all safety tokens using perfect-forward secrecy. For Digi.me (MUMC, Maastro): medmij framework ("MedMij Framework" 2021) If 6 = HTTPS based Note: AIDAVA UI input by the patient may also require encryption if the UI resides outside of the VPN; if this is inside of the VPN - we will use a https certificate.
Infrastructure details.	See technical architecture in next section
Error handling (How errors will be handled during exchange. Include a process flow if required)	 (f 4 = (to be specified by each hospital) MAASTRO/MUMC: HTTP status code to indicate the output of the request. (f 5 = For MIDATA (NEMC, MUG): Traceability of data processing of sensitive data is ensured: Entries are created in the audit log for each security-critical action. The author is saved for each data record and for each update of a data record. The change history for each data record is available. For Digi.me (MUMC, Maastro): The data will be validated by the data manager within the server and the data will be stored within the hospital. Digi.me is not allowed to know the exact location of the data storage according to law. Important point is to not deliver or exchange data directly to the EHR. If 6 = AIDAVA makes detailed logs of everything happening in the system, in case of any error, responsible persons will be notified.

Question	Answer from Data HOLDER				
Issues management - contact details.	 Person responsible for issue management (Data Holder) Name: TBD Role: TBD Person responsible for issue management (Data Recipient) Name: TBD Role: TBD Role: TBD 				
Environment Version Management	 During software development and testing, there is typically three separate environments Development environment: Used by developers, for development, integration and tests. Created and hosted by Partner GND. Test environment: Used by testers from Partner GND, nominated AIDAVA and site administrators have access to do manual testing and configuration. Created by Partner GND on hardware hosted by the medical centre responsible for evaluation. Production environment: The live instance, used by all AIDAVA users, changes only according to change management rules. Created by Partner GND on hardware hosted by the medical centre responsible for evaluation. 				
Data Storage (How and where will data be stored once it is received? May include server names, systems, hosting location and relevant security standards)	 See technical architecture in next section If 4 or 5 = AIDAVA local version in the hospital If 6 = For MIDATA (NEMC, MUG): The platform is hosted in Switzerland, using the Swisscom Dynamic Computing Services (DCS) infrastructure, in Swisscom data centres. DCS is certified according to ISO 20000, 27001, 9001, 14001, ISAE 3402, GDPR (data processor). The database is stored in a replica set with 3 replicates. For Digi.me (MUMC, Maastro): The data storage is in an Azure cloud environment certified by NEN 7510. It is not allowed to be stored as a HDI without the above certification according to MedMij. That wa salso the reason that we selected Brightfish as it is also certified by NEN 7510 for the EQ5D-5L patient questionnaire. 				
Data Security (including disaster recovery and access control)	 If 4 or 5 = procedures in place in the hospital If 6 = For MIDATA (NEMC, MUG): For complete safety and security features, see annex. The database is backed up using the Swisscom Dynamic Storage service, using geo redundant mirroring in several Swisscom data centres. For Digi.me (MUMC, Maastro): According to NEN 7510 and the 				

Question	Answer from Data HOLDER				
	additional Medmij quality certification, there is a data security test yearly done by the NEN 7510 auditor (DNV-GL). The process is evaluated (whether there is a disaster). Penetration test is part of the security test.				
Data Disposal.	 If 4 or 5 = In line with research governance regulations, and taking into account that AIDAVA is a research prototype with no impact on clinical care or clinical research, all patient data transferred to AIDAVA, the resulting curated data (Personal Health Knowledge Graph (PHKG) and the derived data (IPS of the patient, extract to compute CVD score of the patients and BC registry extracts) will be deleted from the system - by Partner GND - at the end of the project, and the solution will be retired. Patients will have the opportunity to ask and receive a copy of their PHKG in electronic format. If 6 = For MIDATA (NEMC, MUG): As a HDI, MIDATA acts in fiduciary capacity on behalf of its data account holders. As data account holders, the 				
	patients have sovereign rights over their encrypted data accounts and the data contained therein. They may export their data, or delete their accounts, or further use the accounts. Data sovereignty of the account holders over the data sets in their data accounts is technically ensured and enshrined in the Articles of Association (https://www.midata.coop/wp-content/uploads/2019/08/MIDATA_Statuten_ 20190626_EN.pdf) and the Privacy Policy (https://ch.midata.coop/#/public/terms?which=midata-privacy-policy); use of the data sets available in the encrypted data accounts by third parties, including MIDATA Cooperative, can only occur with the explicit consent of the account holders. Without such consent, the data cannot be decrypted. For Digi.me (MUMC, Maastro): The aim of the MedMij Agreement System is that anyone who wishes can have access to a Personal Health Environment (PHE) in which - under your own direction - (personal) data and/or information about your health is included. In order to				
	provide the PHE with the (personal) data and/or health information you require, agreements have been made in the MedMij Agreement System about the exchange of this data. The exchange of data between the healthcare provider and your PHE therefore takes place via parties that comply with these MedMij agreements. Pursuant to the Medical Treatment Contracts Act (WGBO), the healthcare provider is obliged to ensure that 'others' than the patient (read: you) have no information about, access to or a copy of your medical file, unless you have given permission for this, has granted. Since your PHE (and any underlying party that works according to the MedMij agreements) is a so-called 'other' (in the sense of the WGBO), you must give the healthcare provider permission for this data				

Question	Answer from Data HOLDER				
exchange. This permission specifically relates to the set of					
	data and health information that, at your request, is exchanged by the				
	healthcare provider - in accordance with the agreements in the				
	MedMij Agreement System - with your PHE.				

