+ 0.0005510715 x (age in	(observable entity)	
years)²		
+ 0.2876587433 [if male]	Answer is Y in case of presence of	Mandatory
	SNOMED: 248153007 Male (finding)	
+ 0.3455832714 [if current	A= last occurrence of smoker SNOMED: <<	Mandatory
smoker]	77176002 Smoker (finding)	(default = N)
	B = last occurrence of	
	Quit-Smoking (<< 160617001 Stopped smoking)	
	OR Ex-Smoker (<< 8392000 Non-smoker)	
	IF time of A is after B,	

¹² Numbers from Dutch population (baseline characteristics from the SMART study); it is valid for male/female and all ages. The same number can be used across the EU population.

Formulas	SNOMED / LOINC Code (available in PHKG)	Population ¹² value if missing
	THEN value is Y FLSE value is N	
+ 0.0018913154 * systolic blood pressure in mmHg	Take last value in PHKG ; SBP= LOINC: 8480-6	Mandatory
	(average value across a period of time)	
+ 0.3181706587 [if diabetic]	Answer is Y in case of presence of SNOMED: << 73211009 Diabetes mellitus (disorder) (and all children codes)	VAL = 17% * 0.223 (average)
+ 0.2947019539 [if history of coronary artery disease, of acute coronary syndrome, myocardial infarction or coronary revascularization]	 Answer is Y in case of presence of SNOMED: << 53741008 Coronary arteriosclerosis (disorder) (and all children codes) OR SNOMED: << 394659003 Acute coronary syndrome (disorder) (and all children codes) OR SNOMED: << 22298006 Myocardial infarction (disorder) (and all children codes) OR SNOMED: << 415070008 Percutaneous coronary intervention (procedure)>> (and all children codes) OR SNOMED: <<232717009 Coronary artery bypass grafting (procedure) >> (and all children codes) 	Mandatory (default = N)
+ 0.3483178604 [if history of cerebrovascular disease, TIA, brain infarction, amaurosis fugax, retina infarction or carotic surgery]	 Answer is Y in case of presence of SNOMED: << 230690007 Cerebrovascular accident (disorder) (and all children codes) OR SNOMED: << 266257000 Transient ischemic attack (disorder) (and all children codes) OR SNOMED: << 432504007 Cerebral infarction (disorder) (and all children codes) OR SNOMED: << 88032003 Amaurosis fugax (disorder) (and all children codes) OR SNOMED: << 175362007 Carotid and/or cerebral and/or subclavian artery operations (procedure) (and all children codes) 	Mandatory (default = N)

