The senior physician will then be able to decide on one of the following reasons for discrepancy. Health record incomplete: the information was not available in the medical record, while it should have been – and therefore AIDAVA could not identify the right value.

- Error in AIDAVA: the information is rightly included in the medical record, but AIDAVA did not include this information properly
- Error from physician: AIDAVA is right and the junior physician evaluation is not correct.

To assess the longitudinal aspects of AIDAVA, the SMART score will be calculated 2 times (after G1 and \pm 16 to 18 months later, at the end of G2 use year follow-up). The aim is to see if modifiable risk factors can be captured and risk can be calculated by AIDAVA automatically and reliably.

4. Study Design

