G1 and G2 VISIT 1 - on site W1 Day 1 (either elective outpatient clinic visit OR inpatient stay during index MI event),	 Approximately up to 50 inpatients screened, 15 inpatients enrolled (Note: Day1 and Day2 may seem busy for a patient recovering from MI; most patients are however recovering well and find difficult to remain in hospital during the monitoring period) 1. Checking I/E criteria (In REDcap) 2. Project introduction (10 min, doctor). Research associate complete REDCap Form (in REDCap, Patient Screening FORM) If the patient meets the criteria and is interested in participating in the project, he/she will move on to the research associate 3. Under supervision of Research Associate - 30-60 min per patient 	

	CVD patients	BC patients
	 a. Share details of the project with patients ; b. Provision of SIP and explanation - including use of EQ-5D QALY - quality of life questionnaire several time c. Introduction of HDI and questions regarding ownership and future use of the data through HDI d. Answer to questions e. Request to read and sign ICF and HDI agreement f. Provide medical device to patient 4. Research associate update REDCap Form (in REDCap, Patient Screening FORM) 5. Confirmation of patient enrollment; 	
	 Create HDI account (through AIDAVA) Questionnaire to specify user profile (In REDCap 3. Training session for the patient on the prototyp Patient fills EQ-5D form through HDI provided a Research associate complete REDCap Form (sources for enrolled patients Patient and expert curator curate medical data), User Profile FORM) e by the research associate pp in REDCap, Patient monitoring FORM) data extraction from different with AIDAVA
W1	CVD patient will use medical device	
Day 2 - 5	 Patient will use AIDAVA and test its functionalities, take notes and if necessary, will contact Helpdesk whenever needed Expert curator will curate the data in AIDAVA on demand. RA fill the patient monitoring form (in REDCap, Patient monitoring FORM) 	
W1 Day 5	 First calculation of SMART risk score by AIDAVA (automatically) and CVD expert (manually). Data collection and entry forms : Documentation of SMART risk score calculation result and time (in REDcap, Patient Monitoring FORM) by RA 	 System extracts the patient data for insertion into the local AIDAVA BC registry Queries identified as secondary end points will be fired automatically by the system and results available for display to the BC data users

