	1. Data curators spreadsheet (Patient as curator and Exper Form)	t Curator), (in REDCap, Patient Curator FORM; Expert Data Curator

	CVD patients	BC patients
	 Data user/consumers spreadsheet (In REDCap Data use AIDAVA extract IPS and forward it automatically to the H monitoring FORM) 	r/consumer FORM) IDI + enter flag in Data collection and entry forms (REDCap, Patient
VISIT 2 - online W2 Day 1	CVD patients use medical device Check if there is any issue with the medical device (CVD patient only)	
	 Second training session on the prototype - online (open Patient and expert curator curate medical data using All RA fill the patient monitoring form (in REDCap, Patient in Complexity) 	questions) DAVA monitoring FORM)
W2 CVD patient will use medical device		
Day 2-5	 Patient will use AIDAVA and test its functionalities, take Expert curator will curate the data in AIDAVA on deman RA fill the patient monitoring form (in REDCap, Patient in AIDAVA) 	notes and if necessary, will contact helpdesk d. monitoring FORM)
VISIT 3 W2 Day 5	 Second calculation of SMART risk score by AIDAVA and CVD expert Data collection and entry forms: documentation of SMART risk score calculation result and time 	
	 AIDAVA extract IPS and forward it automatically to the HDI (+ enter flag in REDCap, Patient monitoring FORM) Patient and curator will fill in the system usability scale questionnaire online (in REDCap, System Usability Scale - SUS FORM) Data curators spreadsheet (Patient and Expert Curator). (in REDCap, Patient Curator FORM; Expert Data Curator Form) Data user/consumers spreadsheet (In REDCap Data user/consumer FORM) 	
W3		At the end of G1 - across all sites - fires the queries identified as secondary end points; RA reports the results in the data users/consumers spreadsheet (in REDCap Data user/consumer FORM).
End of evaluation	Delete personal patient data and PHKG (after finalisation of evaluation report), but keep evaluation score from G1.	
VISIT 4 - online W4	Feedback to patient	

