6.2. Medical Devices (CVD patient only)

Device/app	Notes
BP monitor with Afib detection	Withings BPM Connect
Data Captured	Blood Pressure
Period of use/ Frequency	During the whole evaluation : 3 times a week / 3 times a day
	Afterwards - once a month/ 3 times a day
API Integration	API Guide
Google Fit app	For Android users
Apple Health app	For iOS users
Instruction for use	In case of issue with the value of BP : go to the GP
	In case of issue with the app or the device: go the RA
Instructions in case of defect	Request support from Research Associate
Disposal after end of study	Patient can keep it
	Note: patients withdrawing from the study should return the
	device to the Research Associate/ site
Monitoring of compliance of use	Research Associate

All device deficiencies (including malfunction, use error and inadequate labelling) shall be documented and reported by the investigator throughout the clinical investigation.

7. Participant Discontinuation/Withdrawal

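### The two SMART scores compared for CVD accuracy share no data date: AIDAVA is loaded once at the start of testing, while the physician collects data at W1D5 and W2D5

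*Protocol*

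**What the plan says.** **Transfers.** The transmission row of Annex 4, section 3.2 covers flow 4 (hospital to AIDAVA) and flow 5 (HDI to AIDAVA) and sets their frequency as "Once at the beginning of testing of each generation of the prototype (push from hospital systems into the file share within VPN"). The same cell calls the exchange incremental: "exchange of any data source should be complete", and "additional data sources can be exchanged as they become available during evaluation". It gives flow 6, the outgoing patient summary, two runs, after week 1 and after week 2. The schedule of activities (section 1.3) marks the CVD data extract at W1D1 only.

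**Scoring.** Section 4.4.2 has "First calculation of SMART risk score by AIDAVA (automatically) and CVD expert (manually") at week 1 day 5 and "Second calculation of SMART risk score by AIDAVA and CVD expert" at week 2 day 5. Section 4.4.4 repeats this for returning patients. Under section 3.2.2 the physician collects, analyses and enters the data into a web calculator.

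**Inputs.** For systolic pressure AIDAVA is told "Take last value in PHKG ; SBP= LOINC: 8480-6", with a note in the same row about an average over a period. Total cholesterol, HDL and eGFR use the last value; hs-CRP uses the last value not above 15.

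**Discrepancies.** A senior physician chooses one of three reasons: an incomplete record, a physician error, or "Error in AIDAVA: the information is rightly included in the medical record, but AIDAVA did not include this information properly".

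**Blood pressure.** The monitor is handed over at W1D1 (section 4.4.2) and used "During the whole evaluation : 3 times a week / 3 times a day" (section 6.2).

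**The concern.** CVD Metric 2 in section 3.2.2 is the percentage difference between the AIDAVA score and the physician's score, and section 9.1 sets a target of 80% or more. The comparison measures the tool only if both scorers could see the same data. Here AIDAVA works from what was loaded at W1D1, while the physician may use anything in the record on the scoring day.

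A result or prescription entered in between would make the scores differ even if AIDAVA processed everything it received correctly. Read literally, such a value fits the AIDAVA error reason, because it is in the record and AIDAVA did not include it. Whatever reason the senior physician picks, the raw percentage difference carries the timing effect.

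A second consequence concerns home blood pressure. The monitor is issued on the day of the scheduled extract, so that extract holds essentially no study readings.

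**Working it through.** The protocol states no figure for this effect, so there is nothing to reproduce. The check has two parts.

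**1. Timing, side by side**

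| Step | When | Source |
|---|---|---|
| Flows 4 and 5 into AIDAVA | Once, start of testing | Annex 4, 3.2 |
| CVD extract | W1D1 | 1.3 |
| Monitor issued | W1D1 | 4.4.2 |
| Home readings | Through both weeks: up to 3 × 3 × 2 = 18 occasions | 6.2 |
| First SMART score, both scorers | W1D5 | 4.4.2, 4.4.4 |
| Second SMART score, both scorers | W2D5 | 4.4.2, 4.4.4 |
| Repeat of a source already sent | None scheduled | Annex 4, 3.2 |
| Common data date | None stated | 3.2.2, 4.4 |

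**2. How far one newer value moves the score**

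The code in section 10.6 gives risk = 1 − (1 − 0.1658228)^exp(LP + 0.0463729 − log(ratio)). The regional ratio is not shown and is taken as 1. The patient is assumed: man, 62 years, non-smoker, no diabetes, coronary disease only, 0 years since diagnosis, on antithrombotic treatment, SBP 150 mmHg, non-HDL 4.2 mmol/L, eGFR 65, CRP 8.

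For this patient LP = 0.0419 and exp(0.0419 + 0.0464) = 1.0923, so risk = 1 − 0.8341772^1.0923 = 17.97%.

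Changing one input at a time:

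| Input | Change in LP | exp(change) | New score | Relative change |
|---|---|---|---|---|
| SBP 150 to 125 | 0.0018913 × (−25) = −0.0473 | 0.954 | 17.21% | −4.2% |
| eGFR 65 to 75 | −0.0396752 × 10 + 0.0002186 × (5625 − 4225) = −0.0907 | 0.913 | 16.55% | −7.9% |
| CRP 8 to 3 | 0.1517602 × ln(3/8) = −0.1489 | 0.862 | 15.69% | −12.7% |
| Non-HDL 4.2 to 2.8 | 0.5403642 × ln(2.8/4.2) = −0.2191 | 0.803 | 14.71% | −18.1% |

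**Range.** A second assumed patient (man, 63, SBP 135, non-HDL 3.7, eGFR 75, CRP 2.2, otherwise alike) has a base score of 13.03%:

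- non-HDL 3.7 to 2.2: −23.2%
- CRP 2.2 to 10: +23.6%
- antithrombotic yes to no: +21.5%
- eGFR 75 to 60: +15.2%
- SBP up 20 mmHg: +3.6%

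A 20% change in hazard from blood pressure alone would need ln(1.2)/0.0018913 = 96 mmHg. Laboratory and prescription data drive the effect; blood pressure contributes little. With a common cut-off, the timing difference is zero by construction.

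**The case against.** **The transfer text is less rigid than the once-only line suggests.** It calls the exchange incremental and admits further sources during evaluation. The connected device is listed as a source of its own in section 10.1, so it could be added after W1D1. Section 2.2 mentions a refresh of sources, the screening form in section 10.3.2 asks for the date of the first transfer, and section 4.4.4 reloads everything from scratch at generation 2. A reader might infer that generation 1 home readings never reach AIDAVA, or that section 6's aim of integrating patient-generated data cannot be met. The documents support neither. They support only that no transfer of these readings is scheduled before the generation 1 scores.

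**New values may be few.** No study blood draw is scheduled, and Visit 2 is online, so new laboratory results would come from routine care. Home readings go from device to HDI to AIDAVA, and nothing routes them to the physician's record; if both scorers lack them, no discrepancy follows. The fallback for CRP above 15 removes some acute-phase values. This limits the frequency of the effect but does not remove it.

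**A large gap can be built, but only by assumption.** Moving all four inputs of the first patient together takes 17.97% to 11.26%, a 37% relative drop. That needs four new values, all shifting the same way, none of them taken from the documents. It should not be used as the expected size.

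**The classification is not fixed.** The senior physician sees the source and transformation behind each AIDAVA value and may recognise a timing cause. There is still no category in which to record it.

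**A generation 1 to generation 2 artefact is not shown.** A reader might infer that generation 2 would look better because its patients are stable. Visit 1 may also be an elective outpatient visit, and new generation 2 patients follow the same pathway, so this depends on an unknown patient mix.

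**Annex 4 is a template.** Sites complete the transfer specifications locally. That makes a common rule in the protocol more useful, since sites could otherwise refresh at different times.

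**Conclusion.** The point holds in a limited form. The documents schedule one load per generation and two later scorings, state no common data date, and offer no discrepancy reason for data recorded after the load. Followed as written, CVD Metric 2 can mix data age with tool error.

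The effect arises only when routine care adds a laboratory, prescription or blood-pressure value between transfer and scoring; the documents do not say how often that happens. When it does, one changed value moves the score by about 4% to 18% in the first assumed patient, and by up to about 24% with the larger steps of the second. If accuracy of 80% or more means a relative difference within 20%, which the protocol does not define, a single newer laboratory or prescription entry could use most or all of that allowance. These sizes rest on assumed patients and a regional ratio of 1.

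This is a secondary endpoint and the remedy is cheap, so the change should be made, but the study does not stand or fall on it.

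**What to change.** 1. Set one data cut-off per SMART calculation for both scorers: the date of the latest AIDAVA transfer for that patient, recorded on Form 14. The physician uses only items dated on or before it.
2. Reconcile Annex 4, section 3.2 with the schedule of activities (1.3), the refresh in section 2.2 and the first-transfer fields in section 10.3.2. State a dated refresh of the flow 5 blood-pressure data and the flow 4 laboratory and prescription sources before the W2D5 calculation. In the same edit, settle the number of calculations: section 3.2.2 says two in total, sections 4.4.2 and 4.4.4 give two per generation.
3. Add a fourth discrepancy reason, data recorded after the AIDAVA transfer, which does not count against AIDAVA.

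Cost: one date field and one category in REDCap, and one further run of an existing transfer per patient.
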